## Statistical analysis plan

***All aspects of data analysis/statistics will be directed by [name], the Director of Pediatric Data Analytics for the Kentucky Children's Hospital-Office of Pediatric Research, and [name], the Allen-Anderson Endowed Professor of Department of Statistics, University of Kentucky.***

**Aim 1: Compare efficacy and safety of prophylactic indomethacin, DCC, and their combination, in affecting the incidence and severity of IVH in infants less than 28wks gestational age.**

- **Aim 1A)** Test for differences in **primary outcome measure**: 'fraction of survivors with no severe IVH or PVL' among the 4 treatment groups, using head ultrasound at 1-30d and head MRI at 38wks adjusted gestational age.
- **Aim 1B)** Test the hypothesis that DCC improves effectiveness and/or decreases toxicities of indomethacin.
- **Aim 1C)** Test for treatment dependent differences in neurocognitive follow up evaluations and investigate relationships between short term brain imaging results and later neurocognitive performance across treatment groups.

**Aim 1 Statistical analyses: [all analyses performed as 'intention to treat' where appropriate]:** To investigate the primary hypothesis in Aim 1A (treatment-related outcome differences with respect to the primary endpoint fraction of cases surviving without severe IVH, grade 3 or 4) we will use head ultrasound data from day of life 0-30, and use two distinct approaches. First, based on the qualitative data used to compute the sample size, we will employ a bivariate analysis to identify the significant covariates, followed by a multiple logistic regression analysis to test for differences between the four groups in the presence of significant covariates. Secondly, we will develop severe IVH or PVL data and employ survival analysis statistics (log rank Mantel-Cox test). If the assumptions are validated, we will use the Cox proportional hazard model for this survival data. In addition we will compare head MRI results (measured at the single time point of 38wks adjusted gestational age using a multiple regression model that will incorporate significant covariates. Aim 1B is concerned with comparison of Groups 3 and 4 only (e.g. Indomethacin vs. Indo-DCC) and the procedures developed for the 4 group analysis are also applicable here. For Aim 1C we correlate later performance with the short term brain imaging results in the framework of a multiple regression model where the 4 groups will be used as predictors and will be compared. In all settings we will also perform separate analyses of IVH alone, and PVL alone.

Aim 1 also involves comparisons of nominal/ordinal and continuous variables associated with neurodevelopment and toxicity where single or repeated measures on the response are available. Approaches similar to the one described above will be taken where we first build a statistically valid model that controls for all influential covariates and test the relevant hypotheses in the context of the model. Aim 1B corresponds to the testing of the interaction effect between the ICC/DCC effect and the use of prophylactic indomethacin. Other hypotheses correspond to the main effects. We will also compare the variables that reflect renal function/status (as assessments of potential indomethacin toxicities, other specific comorbidities and hospital stay related variables across the 4 groups.

**Aim 2: Investigate mechanistic effects of prophylactic indomethacin, DCC, and their combination in infants less than 28wks gestational age.**

- **Aim 2A)** Test the hypotheses that blood volume status and/or hemodynamic stability are different between groups (at 0,1,3,7,and 30 days of life).

- **Aim 2B)** Test the hypothesis that biomarkers of inflammation and vascular endothelial stress are different between groups (at 0,1,3,7,and 30 days of life).
- **Aim 2C)** Test the hypothesis that numbers, or apoptotic frequency, of circulating progenitor cells with endothelial or neuronal phenotype capacity are different between groups (at 0,1,3,7,and 30 days of life).

**Aim 2 Statistical analyses: Comparisons of biochemical and hemodynamic variables across treatments:** For Aim 2 we compare the blood sample variables (Hct, HB, Ferritin, CRP, IL6, TNF, s-ICAM, progenitor cell numbers, and apoptotic cell percentages) and summary measures of cardiovascular variables (blood pressure, pressor support and others) using a multivariate linear regression model (for continuous responses) and a multivariate logistic regression model (for nominal variables such as the need for inotropic/vasopressor support) regression analyses where influential demographic variables associated with mothers and infants will be used as covariates. The differences in the pattern of changes over time of the repeatedly measured cardiovascular status variables such as the blood pressure levels will be examined using repeated measures Analysis of Variance techniques and mixed effect ANOVA models. Influential covariates will be used for building a suitable predictive model using variable selection methods to identify the optimal variable set. Using this model, the hypotheses regarding the differences between the 4 groups and their interaction effect with time will be examined.

**Aim 3: Determine relationships between clinical outcome measures (Aim1) and blood measurements (Aim 2) among treatment groups.**

**Aim 3 Statistical analyses:** We will use our complete data set to investigate predictors of brain injury (IVH, or PVL), predictors of poor neurocognitive outcomes and the influence of treatment group on these predictive variables. Ultimately we will use the data collected in this project to identify which of our measured variables are the most 'useful' from a clinical perspective in forecasting outcomes in these high-risk patients. Significant variables for prediction will be identified using bivariate methods. Correlations will be utilized for two continuous variables. ANOVA, independent samples t-tests and independent samples nonparametric methods will be employed as appropriate for a nominal explanatory variable and a continuous variable. Pearson's chi-square and Fisher's exact statistic will be used as appropriate when both variables are nominal. For each outcome variable, appropriate multivariate modeling will be constructed using the identified significant variables from the bivariate analysis along with the grouping variables to ascertain the best reduced models for prediction. An alpha level of 0.05 is used for inclusion into the models. Any non-normally distributed continuous data will be corrected through appropriate transformations. Statistical software SAS 9.4 (SAS Institute, Cary, NC) and IBM SPSS Statistics (IBM Corp., Armonk, N.Y., USA) will be used for analyses. We have powered our study using chi-square tests for equality of proportions, but adopted analysis strategy that controls for influential covariates will generally improve the power. ***In all settings we will also perform separate analyses of IVH alone, and PVL alone.***

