## Study Protocol:

### 1. Objectives:

**Primary GOAL:** Compare efficacy and safety of prophylactic indomethacin, DCC, and their combination, in affecting the incidence and severity of IVH in infants less than 29wks GA at birth.

- **Aim 1A):** Test for differences in primary outcome measure: 'fraction of survivors with no severe IVH or PVL' among the 4 groups, using head ultrasound (1-30d), and head MRI at 38wks adjusted GA.
- **Aim 1B):** Test the hypothesis that DCC improves effectiveness and/or decreases toxicities of indomethacin.
- **Aim 1C):** Test for treatment dependent differences in neurocognitive follow up evaluations and investigate relationships between short term brain imaging results and later neurocognitive performance across treatment groups.

**Secondary GOAL:** Investigate mechanistic effects of prophylactic indomethacin, DCC, and their combination in infants less than 29wks GA.

- **Aim 2A):** Test the hypotheses that blood volume status and/or hemodynamic stability are different between groups (at 0,1,2,3,7, 30, and 60 days of life).
- **Aim 2B):** Test the hypothesis that biomarkers of inflammation and vascular endothelial stress are different between groups (at 0,1,2,3,7, 30, and 60 days of life).
- **Aim 2C):** Test the hypothesis that numbers, or apoptotic frequency, of circulating progenitor cells with endothelial or neuronal phenotype capacity are different between groups (at 0,1,2,3,7, 30 and 60 days of life).
- **Aim 3):** Determine relationships between clinical outcomes (Aim1) and blood measurements (Aim 2) among treatment groups.

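### The SAP's analysis text restates the primary endpoint without PVL or MRI, and the denominator, the handling of death and the deciding test are not fixed

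*Combined protocol and SAP*

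**What the plan says.** Protocol section 1 (Objectives), Aim 1A, gives the primary outcome as "fraction of survivors with no severe IVH or PVL' among the 4 groups, using head ultrasound (1-30d), and head MRI at 38wks adjusted GA". The Statistical analysis plan repeats it under its own Aim 1A: "fraction of survivors with no severe IVH or PVL' among the 4 treatment groups, using head ultrasound at 1-30d and head MRI at 38wks".

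The paragraph headed Aim 1 Statistical analyses then states the primary endpoint for the same aim as "fraction of cases surviving without severe IVH, grade 3 or 4) we will use head ultrasound data from day of life 0-30". It lists two approaches:

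- The first is a multiple logistic regression, introduced as "based on the qualitative data used to compute the sample size".
- The second is time-to-event: "we will develop severe IVH or PVL data and employ survival analysis statistics (log rank Mantel-Cox test", with a Cox model if its assumptions hold.

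MRI enters as a further comparison: "In addition we will compare head MRI results". PVL also has its own analysis: "In all settings we will also perform separate analyses of IVH alone, and PVL alone". The paragraph's heading applies intention to treat, qualified as holding where appropriate. The power basis appears under Aim 3 Statistical analyses: "We have powered our study using chi-square tests for equality of proportions".

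**The concern.** Both definitions are current text, a few lines apart in the same SAP, and they differ in three ways: whether PVL counts, whether the 38-week MRI counts, and what happens to infants who die.

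The third matters most. A fraction of survivors, read literally, has survivors as its denominator, so deaths drop out. A fraction of cases surviving without the lesion keeps every case, and a death is a failure. A survivors-only comparison cannot detect an effect on mortality. If treatment does affect mortality, it no longer compares the groups that were randomised.

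The second approach adds a further uncertainty. Its event includes PVL, but nothing says whether death is an event or a censoring, or when survival is judged. Neither approach is labelled primary. The main result could therefore depend on which sentence is followed, and that choice could be made after the data are seen.

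**Working it through.** **Texts side by side**

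| Element | Objectives and SAP Aim 1A | Aim 1 Statistical analyses |
|---|---|---|
| Lesion | severe IVH or PVL | severe IVH in the stated endpoint; severe IVH or PVL in the log-rank |
| Imaging | ultrasound days 1-30 and 38-week MRI | ultrasound days 0-30; MRI compared separately |
| Denominator, read literally | survivors | all cases |
| Death in the log-rank | not addressed | not stated |
| Deciding test | not addressed | two approaches, unranked |

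**The plan's own figure.** The documents give 400 infants, 100 per group (section 4), and a chi-square power basis. The supplied text has no event rates, target difference or power, so 400 cannot be reproduced. All rates below are assumptions for illustration.

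**How the denominator alone can change the answer.** Suppose mortality is 10% in one arm and 20% in another, and lesions among survivors are 20% and 10%.

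- Survivors only: 80% vs 90%.
- All cases: 0.90 × 0.80 = 72% vs 0.80 × 0.90 = 72%.

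One reading shows a 10-point difference and the other shows none.

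**Power by endpoint.** Inputs: 100 per arm, four arms, effect in two arms, baseline death 12%, severe IVH 12% and PVL 4%, treated as independent. Test: 3-df chi-square at 0.05, critical value 7.815. Noncentrality is λ = Σ n(p − p̄)² / [p̄(1 − p̄)].

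*Death only, 12% to 5%*

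- Restated endpoint: 0.88 × 0.88 = 0.7744 vs 0.95 × 0.88 = 0.8360; p̄ = 0.8052; λ = 400 × 0.0308² / (0.8052 × 0.1948) = 2.42; power 22.6%.
- All-randomised IVH/PVL composite: multiply by 0.96, giving 0.7434 vs 0.8026; λ = 1.99; power 19.2%.
- Survivors only: 0.88 × 0.96 = 0.8448 in every arm; λ = 0; rejection rate 5%.

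*Severe IVH only, 12% to 5%*

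- Restated endpoint: again 0.7744 vs 0.8360; power 22.6%.
- Composite: power 19.2%.
- Survivors only, 88 per arm: 0.8448 vs 0.95 × 0.96 = 0.9120; p̄ = 0.8784; λ = 352 × 0.0336² / (0.8784 × 0.1216) = 3.72; power 33.5%.

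A simulation with a covariate-adjusted logistic model and a four-sample log-rank agrees within about 2 points. It also shows what the unstated handling of death does to the log-rank, whose event is severe IVH or PVL, with or without death:

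| Change in two arms | Restated | Composite | Survivors only | Log-rank, death censored | Log-rank, death an event (to day 30 / day 60) |
|---|---|---|---|---|---|
| Death 12% to 5% | 22.4% | 18.9% | 5.1% | 4.6% | 11.4% / 17.5% |
| Death 20% to 8% | 52.5% | 45.6% | 5.2% | 4.4% | 25.4% / 41.0% |
| IVH 12% to 5% | 20.9% | 18.2% | 34.2% | 37.0% | 21.0% / 18.2% |
| PVL 5% to 1.25% | 5.6% | 8.2% | 10.0% | 8.8% | 7.4% / 7.6% |

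The simulation detects PVL on the day-30 scan only. Its composite therefore does not quantify an endpoint that also uses the MRI.

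**Two unranked tests.** If either test could support the claim at 0.05, independence would give 1 − 0.95² = 9.75%. In the null simulation (PVL 3% or 5%), either test was significant in 8.8-8.9% with death censored and 7.2-8.0% with death as an event. Using one shared composite for both tests still gave 8.3-8.4% and 6.5-7.4%, so most of the excess comes from having two tests.

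**The case against.** The strongest reply is that the analysis paragraph is shorthand. It names Aim 1A, whose composite is spelled out just above, and separate analyses of IVH and PVL make sense only beside a composite. The intention-to-treat heading, read with the all-cases wording, points to every randomised infant with death as failure. The logistic model is listed first and tied to the sample-size data, and the study was powered on proportions, so the primary test is implied. The sample-size calculation is not in the supplied text and may define the binary endpoint.

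Much of this stands. A reader might infer that PVL has been dropped from the trial; it has not, since it is in the log-rank event and analysed alone. A reader might infer that the plan sets out to exclude deaths; the heading favours the opposite. A reader might also say that nothing indicates a lead test, which is too strong.

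The reply does not close the gap. The heading is qualified, and no passage says that one wording governs the other. Shorthand for the composite would explain the missing PVL more easily than the move of MRI into a separate comparison. Nothing fixes how the log-rank treats death or when survival is judged. An implied ranking of tests does not prevent a later choice between them.

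It is also fair that the powers are low on every reading, that each rests on assumed rates, and that choosing between a mortality-inclusive and a survivors-only endpoint involves a real trade-off for the sponsor.

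**Conclusion.** The concern holds as a conflict in current text about the primary endpoint, with the denominator, the handling and timing of death, and the deciding test left unfixed. It should be settled before any comparative analysis.

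Death carries most of the weight. Under the assumed rates, a mortality-only change from 12% to 5% has about 22% power on the restated endpoint, 19% on the all-randomised composite and 5% among survivors. An IVH-only change of the same size has about 21%, 18% and 34%. These figures are illustrative, but one direction does not depend on them: a survivors-only proportion cannot register a pure mortality effect. Omitting PVL from the stated endpoint changes little by itself (5.6% vs 8.2% power for a four-fold cut from 5%). The effect of leaving out MRI has not been quantified.

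A reader might infer that the plan runs a 7-9% false-positive rate. That follows only if either test may support the claim, a rule that no passage states or excludes.

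**What to change.** Write one primary endpoint in identical words in the Objectives, SAP Aim 1A and Aim 1 Statistical analyses: among all randomised infants, survival without grade 3-4 IVH or PVL. Count death by a stated time point as failure, use the ultrasound and MRI sources that Aim 1A names, and state how a survivor without the MRI is classified.

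Name the logistic comparison of proportions as the single primary test at 0.05, consistent with the power basis. Make the log-rank and Cox analyses supportive, on the same endpoint with death as an event. Keep IVH alone and PVL alone as secondary.

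Separately, reconcile section 6. It says that four ultrasounds, including day 14, are obtained from each subject, but also that the 14-day scan depends on the 7-day findings. The endpoint should rest on the same set of scans in every infant.

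The cost is wording in the protocol and SAP. The second test loses any claim to primary status. Counting death as failure lowers power for an IVH-only effect relative to survivors only (about 34% to 18% in the illustration), and adding PVL costs about 3 points if treatment does not affect it (22% to 19%, or 21% to 18%). Power should therefore be rechecked for the chosen endpoint, including the MRI.

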In summary, a total of 3.7 ml of blood (7 time points during the 0-60 days of life, 0.5mL each, and 2 time points with 0.1ml each), 4 head ultrasound measurements (day of life (DOL) three, first week of life, DOL fourteen and at 30 DOL or later), a head MRI at 38 weeks corrected GA will be obtained from each subject as well as 3 measurements of neurodevelopment (TIMP and Bayley III). Enrolled patients will receive a study number to protect confidentiality of demographic information. Data to be collected is shown on the attached data collection instrument. Only the Co-PIs and study coordinators will know the identities

of the patients and be responsible for the storage of collected data. All data will be de-identified.

Studies shown below are marked as part of standard care or research. The 14 day ultrasound is variable, depending on findings on the 7 day ultrasound. Our standard unit policy is to repeat at 14 days if our routine 7 day ultrasound shows a significant hemorrhage.

Timeline	Procedure	Standard Care	Research
at delivery	umbilical cord blood collection (1-5mL)		X
At admission, 24, 48, & 72hr, Days 7, 30, & 60	blood draw (0.5mL) at each time point	X	
72 hours	head ultrasound		X
7 & 30 days	head ultrasound	X	
7 & 30 days	Serum Cystatin C (0.1mL)		X
14 days	head ultrasound	X	X
Days 30 & 60 if not on vent, or as soon as possible when extubated	neonatal sleep study/pneumogram		X
38 weeks of corrected GA*	head MRI*		X
3-4 months of corrected GA	Test of Infant Motor Performance (TIMP)	X	
6-9 months of corrected GA	Bayley III	X	
18-24 months of corrected GA	Bayley III; Brief infant Toddler Social Emotional Assessment (BITSEA), MCHAT(pass/fail)	X	

\* , Please note that at the initial start of this 5 year study our plan for head MRIs in all enrolled patients is considered a research effort. Note however that the use of head MRI in extremely premature infants that are known to or suspected to have brain lesions is currently common-place and at other institutions is standard care. Therefore it is possible (and perhaps likely) that the routine use of this imaging modality will in coming years become 'standard care' for all preterm infants that are at very high risk of cranial bleeds (e.g. the exact patient group in this study) at our institution. If this becomes the case we will provide amendments to the IRB to account for this issue.

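### The Aim 1 covariate rule selects by significance, does not keep out variables that treatment may affect, and does not guarantee adjustment for gestational age

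*Combined protocol and SAP*

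**What the plan says.** The rules are in the Statistical analysis plan part of the combined document.

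- **Primary model** (Aim 1 Statistical analyses, first paragraph): "we will employ a bivariate analysis to identify the significant covariates, followed by a multiple logistic regression analysis", the purpose of the second step being "to test for differences between the four groups in the presence of significant covariates". The MRI comparison also brings in significant covariates, and Aim 1B reuses the four-group procedures on Groups 3 and 4.
- **Other Aim 1 endpoints** (second paragraph): "we first build a statistically valid model that controls for all influential covariates".
- **Aim 2 regression models**: "where influential demographic variables associated with mothers and infants will be used as covariates". This is the only place where covariates are limited by type.
- **Entry level**, given under Aim 3: "An alpha level of 0.05 is used for inclusion into the models".
- **Post-birth measurements**: the table in Section 6 lists blood draws "At admission, 24, 48, & 72hr, Days 7, 30, & 60". Aim 2 analyses "Hct, HB, Ferritin, CRP, IL6, TNF, s-ICAM, progenitor cell numbers, and apoptotic cell percentages", together with blood pressure and pressor support, as responses to treatment.
- **Gestational age** is an eligibility criterion in Section 3. Section 2 describes blocks of 8 and states no strata. The SAP does not name gestational age as a covariate.
- **Reason for adjusting** (end of Aim 3): controlling for covariates is expected to raise power above that of the chi-square test used for sample size.

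**The concern.** A screen against the outcome picks whatever predicts the outcome, whenever it was measured. This trial records many variables after the cord is clamped and the study drug started. Aim 2 asks whether they differ between groups, and Aim 3 asks whether they relate to clinical outcome. If both answers were yes because treatment acts through the variable, it would be a mediator. A group comparison that conditions on a mediator estimates only the part of the effect that bypasses it, not the effect of assignment. Because the ultrasound window runs to day 30, a value drawn late in it could also be a consequence of haemorrhage.

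There are two lesser problems. Adjustment for gestational age depends on its p-value in the same data. And the model behind the primary test is not known until the outcomes have been seen.

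**Working it through.** **1. The plan's own figure.** The plan states 400 infants, 4 × 100. The available text gives no event rates, effect size or target power, so this cannot be reproduced. For orientation only: 75% v 90% needs 100 per group for 80% power (two-sided 0.05, no continuity correction), but many other pairs of rates could underlie the number. The plan states no figure for the consequence of its covariate rule.

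**2. Side-by-side reading.** Aim 1 has a selection rule (significance, or influence) and no limit on candidates. Aim 2 has a limit (demographic variables), but nothing carries it to Aim 1. Aim 1C regresses later performance on early imaging with the four groups as predictors in the same framework. So the SAP does not reserve models containing treatment group for pre-treatment variables.

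**3. Four-group illustration.** All effect sizes here are assumptions. D and I indicate DCC and indomethacin, M is a post-birth marker, GA is gestational age in SD units, and m is the share of the effect carried by M.

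- M = 0.5(D + I) + N(0,1)
- logit P(good outcome) = logit(0.70) + ln(1.8)(1 − m)(D + I) + [ln(1.8)·m/0.5]·M + ln(1.5)·GA
- Screen: univariable logistic Wald test, |b/SE| > 1.96
- Group test: likelihood ratio on 3 df at 0.05; 1,500 runs per row

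| m | M enters | Power, GA forced in, M excluded | Power, screened model | Combination-arm log OR, forced → screened |
|---|---|---|---|---|
| 0% | 18.6% | 78.8% | 75.5% | 1.22 → 1.19 |
| 25% | 90.2% | 78.1% | 49.6% | 1.19 → 0.92 |
| 50% | 100% | 75.9% | 22.2% | 1.13 → 0.59 |
| 80% | 100% | 70.1% | 7.0% | 1.04 → 0.24 |

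Check at m = 50%: the direct log OR in the combination arm is 2 × ln(1.8) × 0.5 = 0.588, and the screened model gives 0.594.

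**4. Other assumptions.** Two further set-ups followed a DCC effect in 400 infants.

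| Events | m | OR, baseline-only → screened | Power, baseline-only → screened |
|---|---|---|---|
| about 15% | 30% | 0.47 → 0.58 | 69% → 38% |
| about 15% | 50% | 0.49 → 0.68 | 68% → 24% |
| about 16% | 30% | 0.49 → 0.58 | 66% → 43% |
| about 16% | 50% | 0.50 → 0.68 | 67% → 23% |

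With no mediation, the loss across the three set-ups was 0 to 6 points (for example 69% v 63%). The result depends on how far treatment shifts the marker. With a 1 SD shift, the marker entered in 91% of runs at 50% mediation and 69% at 30%. At 10% mediation, power was about 70–73% v 57–65%.

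**5. Gestational age.** Chance that it fails a 0.05 screen, assuming 80% good outcomes (2,000 runs):

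| OR per SD | N = 400 | N = 200 (Groups 3 and 4) |
|---|---|---|
| 1.3 | 44% | 68% |
| 1.5 | 11% | 38% |
| 2.0 | about 0% | 4% |

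**6. Chance entries.** The probability that at least one of k independent null candidates passes is 1 − 0.95^k: 23% for k = 5, 40% for k = 10, 64% for k = 20.

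**The case against.** The best defence is that the authors meant baseline covariates. Nowhere is haematocrit, blood pressure or pressor support offered as an Aim 1 covariate. The SAP treats them as responses in Aim 2 and as predictors of injury in Aim 3, and Aim 3 would be partly redundant if Aim 1 had already absorbed them. The stated reason for adjusting, more power, fits baseline prognostic factors. The sentence also ties the screen to the qualitative data behind the sample size. That could mean a restricted data set, and neither the sample-size calculation nor the data collection instrument is in the text available here.

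Much of this stands. A reader might infer that the plan will adjust for mediators, or that the primary result will be masked. The documents support neither reading: they leave the door open and no more. Nor do they assert that treatment works through these variables; Aim 2 tests whether they differ. The mediated share, event rate and effect sizes above are all assumed. The gestational-age part is weak for the whole trial, since a strong predictor would nearly always pass at 400. The second approach to the primary hypothesis includes a log-rank test, which is unadjusted and does not share the problem, although a Cox model with selected covariates might.

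What does not stand is that the limit is already there. The demographic wording covers Aim 2 only, and an intention that is not written down does not bind the analyst.

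**Conclusion.** The concern holds as a gap in specification. The Aim 1 rule selects covariates by significance, does not exclude variables that treatment may affect, and does not ensure adjustment for gestational age. If a mediator were screened in, the estimate would move toward no effect. At 25–50% mediation, power falls from about 66–78% to about 22–50% under the assumptions shown; with no mediation the cost is about 0–6 points. These figures illustrate a conditional risk and do not forecast this trial's power. The point does not rest on any claim of inflated false positives. The gestational-age gap matters most where Aim 1B is read as Groups 3 v 4: at 200 infants and an odds ratio of 1.5 per SD, gestational age would be left out 38% of the time. The SAP also describes Aim 1B as an interaction test, for which the 200-infant figure does not apply.

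**What to change.** In Aim 1 Statistical analyses, replace the bivariate screen for every between-group test (logistic, Cox, MRI and Aim 1B) with a short prespecified list that enters whatever its p-value. The list should hold gestational age at birth as a continuous term and, at the sponsor's choice, other characteristics that treatment cannot affect, such as sex. Apply the same list where the second paragraph refers to influential covariates.

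State that no variable that cord clamping or study drug could affect enters a treatment-effect model. Do not word this as a ban on anything measured after randomisation: Section 4 has the allocation card opened before birth, so that wording would exclude gestational age at birth and sex. Mode of delivery may not be settled when the card is opened, so it needs thought before it is listed.

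Keep screening for the Aim 3 prediction models. In Aim 1C, keep the model relating imaging to later performance separate from the treatment comparison, which should not adjust for imaging.

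The cost is a change of wording. The downside is that a covariate with little prognostic value may use a degree of freedom. If baseline covariates were always intended, this only writes the intention down.

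### The log-rank/Cox approach to Aim 1A names only severe IVH or PVL as its event and has no rule for death, although the endpoint it tests requires survival

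*Combined protocol and SAP*

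**What the plan says.** The protocol (section 1, Objectives) words the primary outcome as "fraction of survivors with no severe IVH or PVL' among the 4 groups, using head ultrasound (1-30d), and head MRI at 38wks adjusted GA". The SAP's Aim 1A statement repeats the core of this: "fraction of survivors with no severe IVH or PVL' among the 4 treatment groups".

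The SAP text under Aim 1 Statistical analyses restates it as the "primary endpoint fraction of cases surviving without severe IVH, grade 3 or 4". For that hypothesis, "we will use head ultrasound data from day of life 0-30, and use two distinct approaches". The first approach is a logistic regression adjusted for covariates. The second is "Secondly, we will develop severe IVH or PVL data and employ survival analysis statistics (log rank Mantel-Cox test", followed by "If the assumptions are validated, we will use the Cox proportional hazard model for this survival data".

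The scans that can show a lesion are scheduled in protocol section 6: "4 head ultrasound measurements (day of life (DOL) three, first week of life, DOL fourteen and at 30 DOL or later". The analysis set is given as "all analyses performed as 'intention to treat' where appropriate". The documents state no time origin, event time, censoring rule or handling of death for the survival analysis.

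**The concern.** Both approaches are offered for the same hypothesis, so they should score the same infant the same way. In the SAP's analysis wording, success requires survival and the denominator is cases, so a death is a failure. The only event named for the log-rank and Cox analyses is a lesion. If an analyst builds the data set from that wording and follows the usual default, an infant who dies without a recorded lesion leaves the risk set as censored.

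The survival analysis would then compare lesion hazards among infants still alive. A treatment that reduced lesions while raising early deaths could look beneficial, and one that changed only survival could look inert. The SAP also has no rule for the case where the two approaches disagree. If the handling of death is settled after the data are seen, a result on the primary hypothesis becomes open to choice.

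**Working it through.** **1. The plan's own figures.** None bears on this point. The sample size of 400 (100 per group) is said to rest on chi-square tests, but no event rates, effect size, power or test level are given. It cannot be reproduced, and the point does not depend on it.

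**2. Typical infants under each rule.** The log-rank column assumes the usual default for a lesion-only event.

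| Infant | SAP analysis wording (cases surviving without severe IVH) | Survivors-only reading of Aim 1A | Lesion-only log-rank |
|---|---|---|---|
| Severe IVH on day 3 scan, survives | failure | failure | event, day 3 |
| Dies day 10, clean scans | failure | left out | censored, day 10 |
| Dies day 2, no lesion recorded | failure | left out | censored before the first scheduled scan |
| Severe IVH on day 3, dies day 10 | failure | left out | event, day 3 |
| Alive day 30, clean scans | success | success | censored, day 30 |

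The log-rank departs from the first reading in rows 2 and 3. It departs from the survivors-only reading in rows 2 to 4, because it keeps those infants at risk, or counts them, until they die.

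**3. Infants affected (assumed rates).** Affected infants = 400 × rate of death without a lesion. At 5%, 10% and 15% this is 20, 40 and 60. With an assumed lesion rate of 15%, their share of all failures is 0.05/0.20 = 25%, 0.10/0.25 = 40% and 0.15/0.30 = 50%.

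**4. What is estimated.** Assume constant hazards over 30 days, 20% lesions and 10% deaths without a lesion. Alive and lesion-free: 1 − 0.20 − 0.10 = 0.70. Kaplan-Meier lesion-free with deaths censored: 0.70^(0.20/0.30) = 0.788. Lesion-free among survivors, if every infant with a lesion survives: 0.70/0.90 = 0.778. The censored estimate is well away from the first quantity. It is close to the last in this example, but is not the same quantity.

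**5. Rejection rates (simulated, assumed rates, level 0.05).** Lesions are detected on days 3, 7, 14 and 30 with probabilities 0.5, 0.3, 0.1 and 0.1. Of deaths without a lesion, 40% fall before day 3 and the rest uniformly over days 3-30. Ranges are over repeated runs. Entries are two-sided rejection unless marked.

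| Lesions; deaths without lesion | Comparison | Lesion-only event | Lesion or death |
|---|---|---|---|
| 20% v 10%; 5% v 15% (failures 25% in both) | 200 v 200 | 0.71-0.75 | 0.04 |
| same | four groups of 100 | 0.58-0.59 | 0.06 |
| same, benefit declared | 100 v 100 | 0.44-0.46 | 0.02 |
| 15% in both; 5% v 15% (failures 20% v 30%) | 200 v 200 | 0.08 | 0.65-0.67 |
| same | four groups of 100 | 0.06 | 0.49-0.51 |
| same, harm detected | 100 v 100 | 0.03-0.04 | 0.39 |
| equal lesions; 9% v 11% | 200 v 200 | 0.05-0.06 | 0.07-0.09 |
| 20% v 10%; 8% in both | 200 v 200 | 0.79-0.81 | 0.61-0.63 |

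Here 200 v 200 is the margin of one factor, four groups of 100 is the Aim 1A comparison, and 100 v 100 is the size of the Aim 1B comparison of Groups 3 and 4, to which the SAP applies the same procedures.

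**6. A different timing model.** With constant hazards and 100 v 100, lesions 20% v 8% offset by deaths 10% v 22% give 0.65 (lesion-only) against 0.05 (composite). Lesions 15% in both with deaths 10% v 25% give 0.06 against 0.63. The pattern does not depend on one timing assumption.

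**The case against.** Four points on the other side carry weight.

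- **The plan does not say that deaths are censored.** A reader might infer a stated rule that scores these infants as lesion-free. The text is silent, and because it introduces the analysis as a test of surviving without severe IVH, a lesion-or-death event could be fitted to it. This stands. What remains is that the only event named is a lesion, and the default that follows from it conflicts with the endpoint.
- **The Aim 1A endpoint is not settled.** A reader might infer that it plainly counts deaths as failures. That holds for the SAP's analysis wording only. The Aim 1A statements in the protocol and SAP can also mean a proportion among survivors. This stands, but does not rescue the analysis: a lesion-only log-rank does not match that reading either.
- **A lesion-only log-rank is a legitimate test.** With deaths censored it validly compares cause-specific lesion hazards, and that does not need death to be independent of bleeding. The complaint is that it answers a different question from the one it is assigned, not that it is invalid.
- **Its role may be modest.** The survival analysis is listed second, with no decision rule. The study is powered on proportions, and the logistic regression can already count deaths. To call the log-rank a primary analysis in its own right would go beyond the text.

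The death contrasts that drive the large figures are also fairly extreme: 5% v 15% is a threefold difference with no support in the documents.

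**Conclusion.** The point holds in a limited form. The second approach to the Aim 1A hypothesis names an event that leaves out death and supplies no rule for it, while the endpoint in the same paragraph requires survival. Under the usual default, the analysis tests a different quantity, and the two approaches can disagree through scoring alone.

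The documents do not establish that any infant will in fact be scored wrongly, and no size can be derived from them because they give no lesion or death rates. Under assumed rates the effect runs from negligible (deaths 9% v 11%, equal lesions) to decisive (deaths 5% v 15% offsetting a lesion difference). It matters most if an intervention affects early death. It should be corrected before analysis, but it does not undermine the trial, since the logistic regression remains as the first approach.

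**What to change.** 1. State the primary endpoint once and use it throughout: all randomised infants as the denominator and death as a failure, which is how the SAP's analysis text reads. Reconcile at the same time whether PVL belongs to it, since that text names only severe IVH while the Aim 1A statements include PVL.
2. In the SAP's Aim 1 analysis text, define the time-to-event outcome along these lines: the event is the earlier of death from any cause and first detection of severe IVH or PVL (PVL subject to item 1); time runs from birth; infants alive with no lesion are censored at their last scan within days 0-30.
3. If a time analysis of lesions alone is wanted, label it secondary and cause-specific, and report cumulative incidence with death as a competing event (Aalen-Johansen curves, Gray test).

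The cost is a few sentences of SAP text. The date of death must be recorded, because a binary endpoint needs only vital status. If a treatment affects lesions only, counting deaths dilutes the comparison: power falls from about 81% to 61-63% at 200 v 200 for lesions 20% v 10%, with an assumed 8% dying without a lesion. The secondary analysis in item 3 keeps the lesion comparison available.
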